9.9 Secondary efficacy analysis

9.9.1 Bayesian analysis of the longitudinal ordinal outcome scale

This data will be analysed using the exemplar analysis plan for “Sequential parallel-group RCTs for COVID-19” published by the FDA center for Drug Evaluation and Research Office of Biostatistics, with the extension to longitudinal ordinal outcomes

[<http://hbiostat.org/proj/covid19/bayesplan.html>], and using the worked example

[<https://hbiostat.org/proj/covid19/orchid.html>]. In brief, a longitudinal ordinal model will be generated including age, sex, presence of diabetes, presence of coronary artery disease, and site. Priors and model decisions will follow the worked example as closely as possible.

The benefit of a longitudinal ordinal model is that as compared to a simple time-to-event analysis, full use of the available data is made. Simulations suggest the effective sample size can be increased by a factor of 5 with the addition of longitudinal data over 28 days

[<https://hbiostat.org/R/Hmisc/markov/>].

9.9.2 90-day All-cause mortality (pending protocol change)

This will be calculated in a similar way to 30-day mortality.

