6.7 Schedule of time and events

6.7.1 Scheduled visits

Potential participants (patients within the inclusion criteria presenting with likely or confirmed COVID-19 infection) will be screened by the research team after review by their clinical medical team. Patients will be approached by the research team, the study discussed, and the patient given a participant information sheet (PIS).

Once COVID-19 infection is confirmed, eligible patients will be consented and enrolled by a member of the study team and then randomized using the in-house randomization mobile phone application "1minclusion".

The study team will make a note in the patient's electronic health record (EHR) about the trial, the patient's enrolment, and the randomization arm. For patients randomized to the active arm, the study team will make a request to the clinical team to prescribe the study medications barring any contra-indications to individual medication. This will be confirmed by a review of the EHR by the study team.

Whilst the patient remains in-hospital, follow-up is via electronic patient health records. The study team will ensure that the study blood tests (such as troponin) are added to routine clinical blood samples.

After discharge, patients will receive phone calls at day 30 and day 90 (pending protocol change) by a member of the study team blinded to the randomization arm.

If contact is lost, their GP will be contacted by a member of the study team blinded to the randomization arm to obtain the 30 and 90-day outcomes.

	Recruitment	In-hospital stay (unblinded study team)	Follow-up (blinded study team)	
	Day 0	Every day	Day 30	Day 90 (pending protocol change)
PIS provided to patient	X			
Patient recruited with written consent	X			
Ensure study blood biomarkers are added to routine clinical blood draws	X	X		
Ensure blood biomarkers and outcomes are entered in the eCRF			X	X
Confirmation of SARS- CoV-2 test positivity	X			
Follow-up telephone call			X	X

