7.1 Intent-to-treat / randomization population

The intent-to-treat population will include all randomized participants in the arms they were allocated to regardless of subsequent treatment received. The analysis will be conducted on an intention-to-treat basis and will include all participants in the arm they were allocated to and for which we have outcome data.

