8.3 Secondary efficacy variables

The key secondary efficacy variable is:

- An ordinal outcome measure (ranging from 1- death to 4 – discharged home)

Other secondary efficacy variables are:

- all-cause mortality at 90-day post randomization collected from in-hospital records and telephone follow up (pending protocol change).
- peak troponin within 7- and 30-days post randomization collected from in-hospital records and data from the NIHR BRC HIC.
- time to discharge from hospital (length of stay) collected from in-hospital records
- need for non-invasive ventilatory support collected from in-hospital records
- need for invasive ventilatory support collected from in-hospital records
- need for mechanical circulatory support collected from in-hospital records
- need for renal replacement therapy collected from in-hospital record

Safety variables

- Bleeding Academic Research Consortium (BARC) bleed event at 30-days post randomization collected from in-hospital records and telephone follow up.
- cessation of randomized active arm therapy from in-hospital records and telephone follow up.
- cessation of randomized active arm therapy due to safety concern from in-hospital records and telephone follow up.

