9.3 Missing data principles

9.3.1 Missing outcome data

The primary analysis will include all participants with known all-cause mortality outcome at 30 days. Significant missingness in mortality data is not expected as outcome data can be obtained from registries. The primary outcome variable will not be imputed in the main analysis.

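### Under the known-outcome rule carried over to 90-day mortality, early deaths always count but survivors randomised before the day-90 call existed can drop out

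*SAP*

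**What the plan says.** Section 9.9.2 gives 90-day mortality no population or missing-data rule of its own: "This will be calculated in a similar way to 30-day mortality".

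The rule it inherits is complete-case on vital status. Section 9.3.1: "The primary analysis will include all participants with known all-cause mortality outcome at 30 days", and "The primary outcome variable will not be imputed in the main analysis". Section 7.1 is to the same effect for the intention-to-treat analysis, which "will include all participants in the arm they were allocated to and for which we have outcome data".

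The day-90 data collection is conditional. Section 6.7.1: "After discharge, patients will receive phone calls at day 30 and day 90 (pending protocol change". Section 8.3 names the sources: "all-cause mortality at 90-day post randomization collected from in-hospital records and telephone follow up (pending protocol change".

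Two other routes to vital status appear. Section 9.3.1: "Significant missingness in mortality data is not expected as outcome data can be obtained from registries". Section 6.7.1: "If contact is lost, their GP will be contacted by a member of the study team blinded to the randomization arm", in order to obtain both the 30-day and the 90-day outcomes.

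The method carried over from section 9.8 is a mixed logistic model reported as odds ratios, with observed mortality tabulated by arm and Kaplan-Meier curves.

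**The concern.** A death by day 30 settles the 90-day outcome without further follow-up. Survival to day 30 does not. For a patient whose day 90 fell before the call was introduced, entry to a known-outcome analysis can therefore depend on the outcome itself.

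Such patients may well exist. Section 5.2 reports that many participants had already gone home within a day or two of randomisation, at a time when the SAP still listed day-90 follow-up as pending. For them, in-hospital records will not generally show status at day 90.

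The fallbacks do not plainly cover them. GP contact is triggered by loss of contact, and a patient who completed the day-30 call and was due no other has not clearly been lost. Registries are mentioned in a paragraph about the 30-day primary analysis and are not listed in section 8.3 as a 90-day source. The 2% allowance for missing outcomes in section 6.6.1 was set for the 30-day endpoint.

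At stake are the 90-day mortality figures by arm, anything a reader derives from them, and under some conditions the odds ratio.

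**Working it through.** **Inputs from the SAP.** Section 6.6.1 assumes 25% control mortality at 30 days and a 20% relative reduction, hence 20% on treatment. Its sample size reproduces: the two-proportion formula at 90% power and two-sided 5% gives 2928 in total, or 3008 with continuity correction, against the stated 3000; and 3000 / 0.98 = 3061.2, rounded up to 3062. There is no SAP figure for 90 days.

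**Assumptions, because the SAP is silent.** *f* is the share of patients randomised too early for a day-90 call. *g* is the share of their day-30 survivors whose day-90 status is recovered. 90-day mortality is taken as 30% vs 24%: true difference 6.0 points, risk ratio 0.80, odds ratio 0.737. Early and later patients have the same risks, and loss does not depend on arm.

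**Formula.** Under the known-outcome rule, each arm shows

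rate = [f(p30 + g(p90 − p30)) + (1 − f)p90] / [f(p30 + g(1 − p30)) + (1 − f)]

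**Half early, none recovered (f = 0.5, g = 0).**
- Control: (0.125 + 0.150) / (0.125 + 0.5) = 0.275 / 0.625 = 44.0%
- Treated: (0.100 + 0.120) / (0.100 + 0.5) = 0.220 / 0.600 = 36.7%

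**Half early, 90% recovered (f = 0.5, g = 0.9).**
- Control: 0.2975 / 0.9625 = 30.9%
- Treated: 0.2380 / 0.9600 = 24.8%

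**Range.**

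| f | g | Control | Treated | Difference (points) | Risk ratio |
|---|---|---|---|---|---|
| any | 1 | 30.0% | 24.0% | 6.0 | 0.80 |
| 5.6% (170/3062, phase 1 minimum, illustrative) | 0 | 31.0% | 24.9% | 6.1 | 0.80 |
| 25% | 0 | 35.4% | 28.8% | 6.6 | 0.81 |
| 50% | 0.9 | 30.9% | 24.8% | 6.1 | 0.80 |
| 50% | 0 | 44.0% | 36.7% | 7.3 | 0.83 |
| 75% | 0 | 60.0% | 52.5% | 7.5 | 0.88 |
| 90% | 0 | 78.5% | 72.9% | 5.6 | 0.93 |

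Both rates are too high whenever f > 0 and g < 1. The difference is usually too large, but at f = 90% it falls below the true 6.0.

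**Odds ratio.** Subtracting numerator from denominator, the known survivors in each arm are (1 − p90)(1 − f + fg). The last factor is the same in both arms and cancels. What remains is a mixture of the 30- and 90-day risks in the numerator. If the risk ratio is the same at both times, the numerators keep that ratio and the odds ratio is exact: 0.737 in every row above. If not, it moves towards the 30-day relative effect. With f = 0.5 and g = 0:
- Equal late deaths (90-day 30% vs 25%): the true odds ratio 0.778 becomes 0.764.
- Effect mostly lost by day 90 (30% vs 28%): control is again 0.275 / 0.625 = 44.0%; treated is (0.100 + 0.140) / 0.600 = 40.0%. The true odds ratio (0.28/0.72) / (0.30/0.70) = 0.91 becomes (0.240/0.360) / (0.275/0.350) = 0.85. The difference goes from 2.0 to 4.0 points and the risk ratio from 0.93 to 0.91.

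In this last case the risk ratio moves away from 1; in the table it moves towards 1.

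**The case against.** The strongest reply is that vital status can be looked up later, so an early survivor's 90-day outcome does not depend on a call on day 90. Section 9.3.1 relies on registries for mortality without an express limit to day 30, and section 6.7.1 has the GP supply 90-day outcomes. Absence of registries from section 8.3 proves little, since section 8.2 does not list them for 30-day mortality either. Moreover, the planned estimate is an odds ratio, Kaplan-Meier curves with censoring would avoid the bias, and the pending protocol amendment may settle who is followed to day 90, after which the SAP may be amended.

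Much of this stands. Loss of survivors is a possibility and not a stated consequence of the plan, and complete tracing removes the bias. What it does not supply is a commitment: nowhere does the SAP say that registry or GP status will be obtained for every early patient, or which patients form the 90-day set. Section 9.9.2 does not specify censoring, and a censored curve could disagree with the proportion tabulated beside it.

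A reader might go further and infer that the plan will inflate the 90-day treatment effect. The SAP does not support that. No absolute difference is planned; the two-stage least squares complier analysis is attached to the primary outcome and is not stated to run at day 90; the direction of error in the risk difference and risk ratio is not fixed; and the odds ratio is exact under a constant risk ratio with loss unrelated to arm.

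**Conclusion.** The point holds in conditional form. Section 9.9.2 imports a rule under which early deaths are always included and early survivors may not be, and nothing in the SAP rules that out. If any such survivors go untraced, tabulated 90-day mortality is overstated in both arms. Under the 30% vs 24% assumption with half the patients early, the overstatement runs from nil (all traced), through about 1 point per arm (90% traced), to 14.0 points in control and 12.7 in treatment (none traced). With only the phase 1 minimum early and none traced, it is about 1 point per arm.

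The odds ratio is safe only under the two conditions shown; in the example where the effect largely fades by day 90, it reads 0.85 instead of 0.91. All these sizes rest on assumed values for 90-day mortality, the early share and the share traced, none of which the SAP gives. This is a secondary outcome, and the 30-day primary analysis is not touched.

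**What to change.** Amend section 9.9.2 in one of these ways, before unblinded data are seen:

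- **Eligibility-defined set.** Include every patient whose randomisation date makes them eligible for day-90 ascertainment, whether or not they died earlier, and leave out all earlier patients, including those who died by day 30. The set is smaller, so the interval is wider.
- **All patients, with censoring.** Include everyone, censor survivors at the date last known alive, and report Kaplan-Meier 90-day risks by arm in place of crude proportions. This assumes that early and later patients have similar risk between days 30 and 90.
- **Full tracing.** If registry or GP status will be obtained for every patient, say so in section 8.3 as the 90-day source and keep the full set. This costs the tracing work but no precision.

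Whichever is chosen, report the number with known 90-day status by arm and by period (before or after the change). The first two options cost only SAP wording.

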9.9.3 Peak troponin and d-dimer within 7- and 30-days post randomization

7- and 30-day peak troponin will be compared between arm by using a linear regression model, including the log transformed baseline troponin including the same baseline variables as the primary model. The methods detailed in Appendix A will be used to incorporate the baseline troponin in the model.

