5.2 Secondary objectives

The secondary objectives are to monitor surrogate markers of efficacy and safety.

The key secondary outcome will be:

- an ordinal outcomes scale (ranging from 1 - dead to 4 – at home)

This outcome was added to the Statistical Analysis Protocol as an amendment (Version 2). The addition of an ordinal outcome scale to the secondary endpoint was made without reference to unblinded data from this trial. This change was based on recommendations from

- Emerging statistical practices of other randomised controlled trials in COVID.
- Public recommendations from various health authorities (WHO) and biostatisticians involved in COVID research.

The motivation to utilise it as the key secondary outcome arose after the DSMB reviewed the data completeness of the blinded troponin and d-dimer data. A significant proportion of patients were discharged home within 1 or 2 days of randomisation. The meant that serial, in-hospital blood results were not able to be obtained and the original planned analysis is untenable.

The secondary efficacy outcomes include:

- mortality at 90 days (pending protocol change)
- peak troponin within 7- and 30-days post randomization
- peak d-dimer within 7- and 30-days post randomization
- time to discharge from hospital (length of stay) from randomisation and from admission
- need for non-invasive ventilatory support
- need for invasive ventilatory support
- need for inotropes or vasopressors
- need for mechanical circulatory support (e.g. ECMO, Impella, IABP).
- need for renal replacement therapy

The secondary pre-specified safety outcomes include:

- Bleeding Academic Research Consortium (BARC) bleed event at 30-days post randomization.
- BARC bleed level 5 (mortality) bleed event at 30-days post randomisation
- thromboembolic event

- adherence to the randomised arm
- cessation of randomized active arm therapy
- cessation of randomized active arm therapy due to safety concern or adverse event

Emerging safety outcomes monitored through:

- Recorded adverse events and serious adverse events

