11 REFERENCES

12 Appendix A: Statistical methods for including troponin level and lower detection limit in the model

Troponin assumed to be a strong predictor of the primary outcome thus it might be associated with the other outcomes as well. Troponin levels, both baseline and peak levels will be log transformed and panned to be added to the models using restricted cubic splines using the methods described by Frank Harrell [<https://discourse.datamethods.org/t/comparing-2-biomarkers-using-restricted-cubic-splines-how-to-interpretation-model-building/663/15>].

We assume a proportion of the measurements will be below the lower detection level. Additionally, the lower detection level could be different between the tests used even for the same patients. To overcome this issue four variables will be used:

- Troponin level: log transformed added as restricted cubic splines (*troponin*)
- Detection indicator variable 1: binary, 1 if there is an available measurement, 0 if measurement was taken but it is below the lower detection level (*detected₁*)
- Detection indicator variable 2: binary, 0 if there is an available measurement, 1 if measurement was taken but it is below the lower detection level (*detected₂*)
- Lower detection level: the threshold level of the given test, categorical or continuous depending on the number of different levels (*detection_level*)

These will be added to the model in the following way for both logistic regression and Cox models:

$$Outcome_i = Treatment_i + minimisation\ variables_i + detected_1 * rcs(\log\ troponin, 3) + detected_2 * detection\ level$$

This method will be used for both baseline and peak troponin levels (if used) depending on the aim of modelling.

The first interaction term (*detected₁ * detection_level*) as a non-zero value if there is a detected troponin and in this case the second interaction term is always zero.

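### Peak troponin is still compared between arms although early discharge defeated serial sampling, and the linear regression has no rule for an undetectable peak

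*SAP*

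**What the plan says.** - **Analysis.** SAP 9.9.3: "7- and 30-day peak troponin will be compared between arm by using a linear regression model, including the log transformed baseline troponin", with the primary model's baseline variables. For detection limits it says: "The methods detailed in Appendix A will be used to incorporate the baseline troponin in the model". The heading names d-dimer, but the text gives no d-dimer model.
- **Feasibility.** SAP 5.2, explaining why the ordinal scale became the key secondary outcome: "A significant proportion of patients were discharged home within 1 or 2 days of randomisation". As a result, "serial, in-hospital blood results were not able to be obtained and the original planned analysis is untenable". The same section still lists peak troponin and peak d-dimer at 7 and 30 days as secondary efficacy outcomes.
- **Source of the values.** SAP 8.3: "peak troponin within 7- and 30-days post randomization collected from in-hospital records and data from the NIHR BRC HIC". SAP 6.7.1: "The study team will ensure that the study blood tests (such as troponin) are added to routine clinical blood samples". Scheduled contact after discharge is by telephone.
- **Detection limits.** SAP Appendix A: "We assume a proportion of the measurements will be below the lower detection level". It adds that limits may differ between tests, even within a patient. Its equation puts troponin on the right-hand side and is written for logistic and Cox models. It also says that both baseline and peak levels are log transformed.
- **Missing data.** Section 9.3.1 deals with missing mortality. Section 9.3.3 imputes a missing detection limit, not a value for an undetectable peak.
- **Interim.** Section 5.3 says the effects on troponin and d-dimer are no longer interim objectives, yet 9.11 still lists peak troponin among the outcomes compared between arms.

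**The concern.** A peak is the largest of however many samples were taken. Here the number of samples is set largely by discharge and death, which are themselves trial outcomes that treatment could change. If one arm goes home sooner, its patients have fewer chances to record a high value, and its peaks look lower with no biological difference. Section 5.2 recognises that early discharge stops serial sampling, but 9.9.3 contains no rule that responds to it. It does not deal with patients who have no post-randomisation sample, or with truncation by discharge or death.

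The second gap is independent of the first. A patient whose post-randomisation samples are all below the limit has a favourable result but no number to enter as the dependent variable. The analyst must drop the patient or substitute a value, and the SAP does not say which.

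At stake is a biomarker comparison that a reader could take as evidence about the cardiac-injury mechanism. The mortality result is not at stake.

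**Working it through.** **1. What the plan states.** The SAP gives no figure for the troponin analysis. Its only size figure is for mortality and is used here as the N for illustration. With 25% against 20%, two-sided 5%, 90% power and 1:1 allocation, n per arm = [1.96·√(2·0.225·0.775) + 1.282·√(0.25·0.75 + 0.20·0.80)]² / 0.05² = 1464, or 2928 in total. With a continuity correction it is 1504 per arm, or 3008. Power at 1500 per arm is 90.7%, and 3000/0.98 rounds up to 3062. The SAP's 3000 and 3062 are reproduced.

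**2. Sampling that stops at discharge.** A simulation of 200 trials per row took N=3000 and no true troponin effect. All remaining inputs are assumptions:
- between-patient SD 1.2 and within-patient SD 0.5 on the log scale;
- exponential length of stay;
- one sample per completed day in hospital, up to 7;
- 20% or 40% of controls home within 2 days;
- stay in the treated arm multiplied by the ratio shown.

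The 7-day log peak was regressed on arm and baseline. The percentage difference is 1 − exp(log difference).

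| Controls home within 2 days | Stay ratio | Log difference | Lower by | False positives | No post-baseline sample |
|---|---|---|---|---|---|
| 20% | 1.0 | 0.000 | 0% | 3.5% | 10.6% |
| 20% | 0.9 | −0.015 | 1.5% | 11.5% | 11.1% |
| 20% | 0.8 | −0.028 | 2.8% | 19.5% | 11.8% |
| 20% | 0.7 | −0.051 | 5.0% | 53.5% | 12.6% |
| 40% | 1.0 | 0.000 | 0% | 3.5% | 22.6% |
| 40% | 0.9 | −0.018 | 1.8% | 9.0% | 23.5% |
| 40% | 0.8 | −0.046 | 4.5% | 36.5% | 24.8% |
| 40% | 0.7 | −0.072 | 6.9% | 73.5% | 26.6% |

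The Monte Carlo standard error of a rejection rate is at most √(0.5·0.5/200) = 3.5 percentage points, so the rates are rough. Death was not simulated, and stay was unrelated to a patient's troponin.

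**3. Undetectable peaks.** Same set-up with equal stays, 20% of controls home within 2 days and a true effect of −0.20 log units. The limit was placed so that a given share of baseline values fell below it. Estimated effect by handling rule:

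| Baseline values below limit | Set to limit | Dropped | Half the limit |
|---|---|---|---|
| 20% | −0.178 | −0.173 | −0.197 |
| 40% | −0.142 | −0.152 | −0.176 |
| 60% | −0.105 | −0.132 | −0.147 |

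The estimate ranges from −0.197 to −0.105. At the extreme, 0.105/0.20 = 52.5% of the true effect remains. Which value is reported depends on a choice the SAP does not make.

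**4. Can Appendix A fill the gap?** Its indicator terms let a model use an undetectable troponin as a predictor. They cannot supply a value on the left-hand side. It does say the method covers baseline and peak levels if used, but the method is still a covariate term, and 9.9.3 invokes it for baseline only.

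**The case against.** The SAP did respond to the missing bloods: it made the ordinal scale the key secondary outcome and dropped troponin from the interim objectives. Peak troponin is now one of several other secondary outcomes, and section 6.6 says p-values are read as a continuous measure of evidence. This limits the weight of the point. It does not supply a rule for data that the SAP itself expects to be absent or censored.

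Several stronger readings are tempting but not supported:

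- **That the SAP calls 9.9.3 itself untenable.** Section 5.2 does not name 9.9.3. What can be said is that 9.9.3 is the SAP's only between-arm troponin efficacy model and relies on the same in-hospital samples. Nor can one say the model was left unchanged, because version 1 is not shown.
- **That peaks would be inflated by 29% or 97%.** With a within-patient log SD of 0.5, going from 3 to 7 samples multiplies the typical peak by exp(0.5·(1.352 − 0.846)) = 1.29, and from 1 to 7 by exp(0.5·1.352) = 1.97. Those figures compare one patient under different sampling. They would be trial bias only if the whole of each arm differed that much.
- **That the arm kept longer will show higher peaks.** This needs stay or survival to differ by arm, and the SAP offers no evidence that it does.
- **That skewed raw values would dominate.** Appendix A says peaks are log transformed; 9.9.3 merely fails to repeat it.
- **That this is the only outcome near the cardiac hypothesis.** Section 5.2 also lists inotropes or vasopressors, mechanical circulatory support and thromboembolic events.

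Ranking deaths worst and using the last in-hospital value for discharged patients looks like an easy remedy, but it still depends on unequal sampling. In a separate simulation under assumed inputs, at a stay ratio of 0.8, it gave 38% to 63% false positives against 23% to 35% for linear regression.

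**Conclusion.** The concern holds in a limited form. The SAP says early discharge prevented the serial bloods its planned analysis needed, yet keeps a between-arm regression of peaks drawn from those bloods. No rule covers undetectable peaks, missing post-randomisation samples, or truncation by discharge or death.

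The sampling bias is conditional. If stays are 10% to 30% shorter in one arm, the assumed inputs give a spurious difference of about 1% to 7%. That is small, but at N=3000 it is enough for a false-positive rate of roughly 10% to 70%. With equal stays only data are lost. The detection-limit gap does not need any difference in stay.

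The sizes are illustrative, because the SAP gives no discharge fraction, undetectable fraction or troponin SD. The existence of the gaps rests on the text alone. This is a non-key secondary outcome; the primary analysis and the sample size stand. The change should be made, because it alters what may be concluded from troponin.

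**What to change.** In 9.9.3:

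1. Label the 7-day peak comparison exploratory and make the 30-day peak descriptive only.
2. State that the outcome is log peak, as Appendix A already says.
3. Replace ordinary linear regression with a model that treats peaks below the assay limit as left-censored at that assay's own limit (Tobit). Alternatively, use a cumulative-probability ordinal model with all values below a common highest limit tied. Adjust for the primary-model covariates.
4. Report by arm the number of samples per patient, the number of patients with no post-randomisation sample, and deaths and discharges before day 7.
5. Add a sensitivity analysis in a fixed early window, for example the first post-randomisation sample within 48 hours. It depends less on length of stay, though not wholly, since some patients leave within that time.
6. Apply the same rules to d-dimer.

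Then align 5.2, 8.3 and 9.11 with this. Section 8.3 omits d-dimer, and 9.11 still compares peak troponin at the interim despite 5.3.

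Item 3 repairs the detection-limit problem only. The sampling problem is managed by items 1, 4 and 5, not removed.

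The cost is SAP wording and slightly more analysis work. The downside is that troponin and d-dimer will support exploratory conclusions only.
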